### **6.3.2. *Definition of Maximum Tolerated Dose and Recommended Phase 2 Dose***

The MTD is the highest dose level meeting *both* of the following criteria:

- It is below the level at which 2 or more patients experienced DLTs during the first 4 weeks of treatment;
- It is a dose level at which no more than 1 patient experienced DLTs during the first 4 weeks of treatment.

The RP2D will be a dose at or below the MTD based on clinical data.

### **6.3.3. *Dose-escalation Enrollment and Review***

Each dose-escalation cohort is expected to enroll at least 3 patients, with a maximum of 6.

- If the initial 3 patients all complete 4 weeks of treatment without a DLT event, the DRC will conduct a dose-escalation review.
- If 1 of the initial 3 patients experiences a DLT event prior to completing 4 weeks of treatment, then enrollment at that dose level will continue to a total of 6 patients and the dose-escalation review will be done when all 6 patients have completed 4 weeks treatment.
- If 2 patients at a dose level experience DLT events during the first 4 weeks of treatment, then no further patients will be enrolled until the DRC completes a review, which should be done as soon as feasible.

Once the last patient in a given cohort has a completed 4 weeks of study treatment, a DRC meeting will be convened to review all safety data and to decide whether to continue or halt dose escalation, or explore intermediate dose levels. To facilitate standardizing the dose-escalation reviews across different cohorts, the focus will be on observations from the first 4 weeks of treatment at that dose level.

The following represent anticipated outcomes for the review process (refer to DRC Charter for full details):

- Dose escalation – progression to the next planned dose level.
- Continue cohort enrollment (applicable only to review after 3 patients) – enroll up to 6 patients at the current dose level to obtain additional safety data for subsequent review.
- Dose de-escalation – enrollment of intermediate dose levels for exploration of other schedules of administration (see [Section 6.5.2](#)).
- Approve enrollment in an expansion cohort at a selected dose level, if applicable (see [Section 6.4](#)).
- No further dose escalation enrollment – at this time the DRC will indicate the dose level that they consider represents the MTD.

## 6.4. Expansion Cohorts

The expansion cohorts provide for additional enrollment at agreed upon dose levels to assess the dose dependence of clinical response.

Once the MTD or a potential RP2D and/or schedule have been established during dose escalation, up to 22 patients will be treated at the RP2D level according to this schedule. The Sponsor may decide at any point during the expansion phase to modify the RP2D based on emerging data including, but not limited to, safety, DLTs, PK, and clinical activity. If such a change is made, enrollment may continue at the selected dose level in up to 22 patients.

## 6.5. Management of Individual Patients

### 6.5.1. Duration of Treatment

Each enrolled patient will receive IMO-8400 at the assigned dose level until the earliest of:

- *Clinical DLT event* – see [Section 6.3](#).
  - Study treatment will be discontinued in patients determined to have a clinical DLT event until resolution and may only be resumed after discussion with an Idera Medical Monitor and agreement that it is in the patient's best interest to continue.
  - For a DME, provision is made for interrupting dosing for up to 3 weeks and, if the acute toxicity improves sufficiently, resuming treatment at a lower dose level based on discussion between the sponsor's designated medical monitor and the treating physician.
  - For DLT laboratory events, provision is made for pausing treatment for up to 3 weeks and, if the acute toxicity improves sufficiently, resuming treatment at a lower dose level (see [Section 6.5.2](#) for details).
  - The Investigator will review with the Medical Monitor decisions to discontinue, pause, and/or restart study treatment.
- *Disease progression* – based on scheduled assessments at Week 1 of each cycle. Unscheduled assessments may be conducted in response to new clinical observations. Disease status will be classified according to international guidelines [1] (see [Section 9.5](#) for details).
- *Termination of participation in the study* – due to AE, withdrawal of consent, intolerable toxicity, or loss to follow up.

In certain instances, patients may be deriving clinical benefit despite objective signs of progressive disease such as radiologic progression. It can be anticipated that based on the study drug's mechanism of action, through an immunologic mediated effect, signs of radiologic response may be delayed. Based on these considerations, continuing to treat some patients past progressive disease may be considered after discussion between the Sponsor and Investigator, provided the following conditions are met:

- Patient has not achieved an objective response on study and then developed progressive disease;

- Patient has not experienced a period of clinically significant stable disease on study and then developed progressive disease;
- Patient must be re-evaluated 4 to 6 weeks after initial progression in order to confirm progressive WM disease;
- If the follow-up assessment does not confirm progressive disease, patient may resume regularly scheduled follow-up per protocol;
- Patient must not have symptoms/signs indicative of clinically significant disease progression;
- Patient must not have a decline in Eastern Cooperative Oncology Group (ECOG) performance status;
- Patient must not have rapidly progressive disease or tumor progression at critical anatomic sites (e.g., cord compression) requiring urgent medical intervention.

#### ***6.5.2. Dose Modification in Patients with Laboratory DLT Events or DMEs***

Patients determined to have a laboratory DLT event or DME ([Section 6.3.1](#)) may resume treatment after dose interruption and with dose modification if *all* of the following criteria are met.

- The patient is receiving  $> 0.6 \text{ mg/kg/week}$ ; patients receiving  $0.6 \text{ mg/kg/week}$  will be discontinued.
- The patient has not previously had dose interruption and/or adjustment for a laboratory DLT event or DME.
- Both the Investigator and the Medical Monitor consider that continued treatment with study drug is in the patient's interest.
- The abnormal laboratory parameter(s) representing the DLT event or DME improve at least 2 grades or back to baseline within 14 days of the last dose administered.

If, for any reason, dosing is interrupted more than 21 calendar days due to toxicity, the patient should be discontinued from study treatment unless the Investigator and the Idera Medical Monitor agree that it is in the patient's best interest to continue.

If dose modification is required, patients should resume dosing at the next lowest dosing level (see [Table-8](#)).

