### 6.2. Dose-escalation Cohorts

The dose escalation cohorts (3 to 6 patients each) will systematically evaluate the safety and tolerability of IMO-8400 at increasing dose levels in order to identify the MTD/recommended Phase 2 dose (RP2D).

- The planned dose escalation cohort levels for IMO-8400 are 0.6, 1.2, 2.4, and 3.6 mg/kg administered once weekly and 1.2 mg/kg administered twice weekly ([Table-8](#)). Additional dose levels, schedules, and routes of administration may be evaluated based upon the emerging data. Weekly exposure is based on body weight (see [Section 8.1](#) for details). Doses will be administered by SC injection.
- For Dose Level 3 (refer to [Table-8](#)), the total dose will be divided into 2 equal portions (1.2 mg/kg twice weekly), administered as separate SC injections over the course of the week, preferably 72 to 96 hours apart (minimum 48 hours) (see [Section 8.4](#) for details).
- Once safety has been established for the 2.4 mg/kg/week as a divided weekly dose (1.2 mg/kg twice weekly), the same dose level of 2.4 mg/kg/week and subsequent dose levels will be given as a once weekly administration.
- Once the RP2D/MTD has been established, patients being treated at lower dose levels may have their doses escalated to the RP2D/MTD upon discussion and agreement between the Sponsor and the Investigator.

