**Table-8. Planned Dose Escalation Cohorts**

Dose Level	IMO-8400 Dose (mg/kg)	Frequency	Initial Cohort Size
1 (starting dose)	0.6	Once Weekly	3-6
2	1.2	Once Weekly	3-6
3	1.2	Twice Weekly	3-6
4	2.4	Once Weekly	3-6
5	3.6	Once Weekly	3-6

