## 8. STUDY TREATMENT

### 8.1. Study Treatments to be Administered

All patients will receive the investigational study drug, IMO-8400, at the weekly exposure level designated for the cohort in which they are enrolled. Instructions for dose preparation are provided in the Pharmacy Manual. Weekly exposure levels are calculated as mg/kg based on body weight at Screening. The dose is to be recalculated if change in body weight from Screening exceeds 10% ( $\pm$ ). Dose volume per injection site should not exceed 1.2 mL/site, with multiple sites used per dose as necessary.

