### **8.4.2. Variances in Dose Administration Schedule**

**Once weekly dosing:** for patients assigned to dose levels of 0.6, 1.2, 2.4, or 3.6 mg/kg/week. The expectation is that patients will be dosed each week on the same day of the week. To allow for holidays and other scheduling issues, individual doses may be administered up to 2 calendar days earlier or later than expected, while remaining on the same schedule. Doses should not be administered fewer than 5 calendar days after the preceding dose.

If, for any reason (e.g., scheduling or toxicity), dosing is interrupted more than 2 calendar days beyond expected, then the next dose should be administered as soon as feasible and the schedule reset to once weekly on the next convenient weekday.

**Twice weekly dosing:** for patients assigned to the dose level of 1.2 mg/kg twice weekly (2.4 mg/kg/week). The total weekly exposure will be administered as a 2 separate SC injections of 1.2 mg/kg per injection, respectively, over the course of the week. The expectation is that patients will be dosed twice each week on the same day of the week, with (approximately) 72 or 96 hours (3 or 4 calendar days, respectively) between injections. The minimum interval between successive doses may not be less than 48 hours (2 calendar days). If, for any reason (e.g., scheduling or toxicity), the interval between successive doses is 6 or more calendar days, then the next dose should be administered as soon as feasible and the twice weekly dosing schedule resumed.

**Extended dosing interruptions.** If, for any reason, dosing is interrupted for more than 21 calendar days due to toxicity, the patient should be discontinued from study treatment unless

the Investigator and the Idera Medical Monitor agree that it is in the patient's best interest to continue.

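### The Section 6.5.2 step-down rule moves a Level 4 patient to Level 3, which halves each injection but leaves the weekly dose at 2.4 mg/kg

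*Protocol*

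**What the plan says.** Section 6.5.1 allows treatment to be paused after a laboratory DLT or a dose modifying event (DME), with provision for "resuming treatment at a lower dose level" if the toxicity improves sufficiently. For laboratory DLTs it refers to Section 6.5.2 for the details.

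Section 6.5.2 gives the rule: when the dose has to be modified, "patients should resume dosing at the next lowest dosing level", with a reference to "Table-8. Planned Dose Escalation Cohorts". That table numbers the levels 1 to 5. Level 3 is 1.2 mg/kg twice weekly and Level 4 is 2.4 mg/kg once weekly.

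Elsewhere the protocol expresses dose by week:

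- Section 8.1 has patients treated "at the weekly exposure level designated for the cohort in which they are enrolled".
- Section 6.5.2 sets its own eligibility threshold for modification in weekly terms: the patient must be receiving more than 0.6 mg/kg/week.
- Section 8.4.2 gives the weekly total of Level 3 in its twice-weekly dosing paragraph, written "for patients assigned to the dose level of 1.2 mg/kg twice weekly (2.4 mg/kg/week".
- Section 6.2 says that, once the divided regimen is shown safe, "the same dose level of 2.4 mg/kg/week and subsequent dose levels will be given as a once weekly administration".

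No section makes an exception for Level 4, and none says whether a lower level means less per injection or less per week.

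**The concern.** The step-down is meant to reduce exposure in a patient who has just had a laboratory DLT or a DME. Read by the row order of Table-8, the rule returns a Level 4 patient to an unchanged weekly dose. Section 6.5.2 also denies modification to anyone who has already had an interruption or adjustment for such an event, so this would be the patient's only adjustment under the stated criteria.

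The rule can also be read in two ways. The table's numbering leads from Level 4 to Level 3. The description in Section 6.2 of the two 2.4 mg/kg/week regimens as the same dose level makes Level 2 the next lower one. Two sites could resume similar patients at weekly doses that differ twofold.

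The data are affected too. Section 10.4.6 has any resumption at a lower level under Section 6.5.2 recorded as a dose decrease. A Level 4 to Level 3 move would therefore appear as a decrease in the safety data although the weekly dose had not changed.

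**Working it through.** **Inputs.** Dose per injection and frequency come from Table-8. The 8-week cycle length is in Section 1.4. Cohort sizes come from Table-8 (3 to 6) and Section 6.4 (up to 22).

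**Weekly dose = dose per injection × injections per week.**

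| Level | Calculation | mg/kg/week |
|---|---|---|
| 1 | 0.6 × 1 | 0.6 |
| 2 | 1.2 × 1 | 1.2 |
| 3 | 1.2 × 2 | 2.4 |
| 4 | 2.4 × 1 | 2.4 |
| 5 | 3.6 × 1 | 3.6 |

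The Level 3 result reproduces the 2.4 mg/kg/week stated in Section 8.4.2.

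**Change at each one-level step = (new − old) / old.**

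| Step | Weekly dose | Dose per injection |
|---|---|---|
| 5 to 4 | (2.4 − 3.6)/3.6 = −33% | (2.4 − 3.6)/3.6 = −33% |
| 4 to 3 | (2.4 − 2.4)/2.4 = 0% | (1.2 − 2.4)/2.4 = −50% |
| 3 to 2 | (1.2 − 2.4)/2.4 = −50% | (1.2 − 1.2)/1.2 = 0% |
| 2 to 1 | (0.6 − 1.2)/1.2 = −50% | (0.6 − 1.2)/1.2 = −50% |

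Level 4 to Level 3 is the only step with no weekly reduction. Dose per injection does not work as the single basis either, because Level 3 to Level 2 leaves it unchanged.

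**Total per 8-week cycle for a Level 4 patient, at full dosing.**

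- Before the event: 8 × 2.4 = 19.2 mg/kg.
- Moved to Level 3: 16 × 1.2 = 19.2 mg/kg.
- Moved to Level 2: 8 × 1.2 = 9.6 mg/kg.

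The ratio between the two readings is 19.2/9.6 = 2.

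**Patients assigned to Level 4.** There are 3 to 6 in escalation. If Level 4 becomes the RP2D, Section 6.4 provides that "up to 22 patients will be treated at the RP2D level according to this schedule", so the maximum is 6 + 22 = 28, before replacements and intra-patient escalation.

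**The case against.** The strongest defence is that Level 3 is lower on the protocol's own ladder. Section 6.5.2 cites Table-8, where Level 3 sits directly below Level 4, and the same-level wording in Section 6.2 describes how escalation proceeds, not how to step down. The divided regimen must be shown safe before 2.4 mg/kg is given once weekly, so the sponsor may regard it as the gentler one, and halving each injection may lower peak exposure. Section 10.4.6 counts a reduction in frequency, strength or amount as a decrease, so weekly dose is not the protocol's only measure. Restart decisions are reviewed with the Medical Monitor, and Section 6.5.2 requires both the Investigator and the Medical Monitor to judge continued treatment to be in the patient's interest.

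Much of this stands. Table-8 numbering is the more natural reading, Level 3 does halve the injection, and central review makes divergence between sites less likely. It does not rescue the rule. The move to Level 3 doubles the frequency and leaves the total amount unchanged, so Section 10.4.6 does not settle the matter. No text states an intention to reduce only the dose per injection, while Section 8.1 and the eligibility threshold in Section 6.5.2 both work in weekly terms. Medical Monitor review does not say which regimen is meant.

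**Conclusion.** The concern holds and is minor. As written, the rule gives a 0% change in weekly dose for a Level 4 patient, against reductions of 33% to 50% at every other step, although Section 6.5.1 provides for a lower dose level. The alternative reading gives half the weekly dose.

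This rests on taking weekly dose as the relevant measure, which Sections 6.2, 6.5.2 and 8.1 support. If peak exposure after each injection drives the toxicity, Level 3 could be a real reduction, but the protocol does not say so. The figure of 28 is a ceiling on patients assigned to Level 4. It does not estimate how many would have a qualifying event and resume, which the document does not give. No harm from the unchanged weekly dose has been shown.

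**What to change.** In Section 6.5.2, define the reduction by weekly dose. Suggested wording: *resume at the next lower mg/kg/week: 3.6 to 2.4 once weekly; 2.4 (Level 3 or Level 4) to 1.2 once weekly; 1.2 to 0.6 once weekly*. Every step then cuts the weekly dose by 33% to 50%, and none raises the dose per injection. The general principle at the start of the sentence would also cover dose levels added later under Section 6.2, which the list itself cannot name.

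If the sponsor does intend Level 4 to Level 3 as a reduction in dose per injection only, Section 6.5.2 should say so and state that the weekly dose is unchanged.

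Either option is one sentence, with no extra patients or procedures. The drawback of the first is that a Level 4 patient takes a 50% weekly cut, because Table-8 has no level between 1.2 and 2.4 mg/kg/week. That is the same proportion as the existing Level 3 to 2 and Level 2 to 1 steps.

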#### ***6.5.3. Management of Systemic Injection Reactions***

Fever, chills, and rigors have been reported in the first 24 hours following IMO-8400 injection. These symptoms have responded well to symptomatic measures without long-term consequences. Prophylaxis with acetaminophen and diphenhydramine may be considered for patients who experience these symptoms with prior injections. Treatment should be discontinued for patients who experience more significant reactions (e.g., anaphylaxis or cardiovascular collapse) and full supportive care provided, as per institutional practice.

#### ***6.5.4. Procedures for Assessment of Patients with Changes in Complement Levels***

Activation of complement in non-human primates is a well-described effect of phosphorothioate oligonucleotides, including IMO-8400. Monkeys are thought to be particularly sensitive to oligonucleotide-induced complement activation and a similar direct oligonucleotide-induced complement activation has not been observed in humans or other species. Specifically, in a 39 week chronic toxicity study conducted in cynomolgus monkeys, 3 of 28 animals administered IMO-8400 at dose levels  $\geq$  6 mg/kg/week were found dead or sacrificed moribund during the study with necropsy findings of myocardial degeneration/necrosis, glomerulonephritis, and/or hepatocellular necrosis. These findings correlated with changes in serum complement levels. Alterations in serum complement in these animals were noted in the weeks to months preceding their unscheduled deaths.

If at any time during study participation, a patient experiences an acute drop in complement (50% hemolytic complement assay [CH50], complement component 3 [C3], or complement component 4 [C4]) levels  $\geq$  50% or a drop to an absolute value below the lower limit of normal with reference to baseline testing or most recent values on study, the following procedures and testing should be performed:

1. Hold study drug treatment
2. Repeat the serum complement test to confirm decreased complement levels
3. Query patient for recent change in signs or symptoms suggestive of a rheumatologic or vasculitic event, i.e. recent appearance of a rash or bruising, new onset symptoms such as fever, arthralgias, or fatigue
4. Perform physical examination with careful attention to findings suggestive of vasculitis; i.e., rash, palpable purpura, petechiae
5. Perform repeat complete blood count (CBC) with platelets, or review most recent CBC/platelets
6. Perform repeat urinalysis, or review most recent urinalysis with special attention to findings suggestive of glomerulonephritis; i.e., presence of protein, blood, red blood cell casts or white blood cell casts
7. Perform an ECG

Based on the results of this work-up and the patient's disease assessment/response to study drug, the Investigator in discussion with the Sponsor's medical monitor, will determine the patient's risk/benefit profile and discuss appropriate next steps regarding the patient's continued participation in the study.

#### ***6.5.5. Procedures for Assessment of Patients with Symptomatic Thrombocytopenia***

Severe thrombocytopenia has been reported in clinical studies with another oligonucleotide [25]. Most of these patients had confirmed anti-platelet antibodies. These cases occurred 14 to 26 months after the onset of treatment, suggesting that risk increases with duration of exposure. In the event of a precipitous drop in platelet counts (i.e., to  $<25 \times 10^9/L$ ), treatment with IMO-8400 should be held and an anti-platelet antibody count obtained. Treatment can be

resumed once pre-treatment criteria ([Section 8.4.1](#)) are met. Antiplatelet, thrombolytic, or anticoagulant drugs should be used with caution.

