## 6.3. Dose-escalation Procedures

### 6.3.1. ***Definition of a Dose-Limiting Toxicity and Dose Modifying Event***

The safety and tolerability of IMO-8400 will be assessed using reported and observed AEs as well as scheduled safety observations including vital signs, physical examination, laboratory tests (hematology, chemistry, and coagulation), urinalysis, and electrocardiograms (ECGs).

A DLT can be either a clinical or laboratory AE.

A potential DLT event is defined as a treatment-emergent AE (see [Section 10.1](#)) which occurs within the first 5 weeks of treatment and meets *any* of the following criteria using NCI CTCAE grading (see [Section 10.4.4](#)):

- Is a clinical event of Grade 3 or higher severity, except for the following:
  - Alopecia
  - Grade 3 fatigue
  - Grade 3 nausea/vomiting that has not been treated with optimal anti-emetic treatments
  - Grade 3 diarrhea that has not been treated with optimal anti-diarrheal treatments
  - AE related to the underlying disease
- Is a confirmed laboratory finding of Grade 3 or higher severity (see [Section 10.4.5](#)) and has been assessed as related to IMO-8400 (any relationship other than “not related”) with the exceptions of neutropenia and thrombocytopenia. DLTs with respect to neutropenia/thrombocytopenia are outlined below:
  - Grade 4 neutropenia lasting > 7 days
  - Grade 3 or 4 neutropenia with a sustained temperature > 101.3° F
  - Grade 3 thrombocytopenia associated with clinically significant bleeding that requires transfusion therapy
  - Grade 4 thrombocytopenia

Clinically significant toxicities or TEAEs that meet the definition of dose-limiting but occurring after Week 5 of Cycle 1 are defined as dose modifying events (DMEs) and may be considered when determining the RP2D.

The Data Review Committee (DRC) is comprised of the Idera Medical Monitor and Investigators from participating sites. The DRC will review all potential DLT events to assess causality, i.e., relationship to study drug (see [Section 10.4.3](#)). Events will be considered DLT events unless they are unanimously assessed as “Not related,” that is, a factor other than study drug is the cause of the event (see [Section 10.4.3](#)).

The definition of a DLT event will be applicable in the following contexts:

- DRC review determining dose escalation (see below).
- DRC review in defining the MTD (see below) or RP2D.

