### **8.4.1. Pre-Treatment Criteria**

IMO-8400 should not be administered until the following conditions are met:

- Hemoglobin  $\geq 7.5$  g/dL
- ANC  $\geq 1,000/\mu\text{L}$
- Platelets  $\geq 50,000/\mu\text{L}$
- All other laboratory abnormalities to baseline or grade  $\leq 1$

These parameters will be measured at local laboratories at Week 1 and Week 5 of each cycle.

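### After a Grade 4 platelet fall, section 6.5.5 permits restart on laboratory criteria alone, whereas 6.5.2 requires discontinuation at 0.6 mg/kg/week and a restricted, stepped-down restart at higher levels

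*Protocol*

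**What the plan says.** Protocol section 6.5.5 covers a precipitous platelet drop, with below 25 x 10^9/L as the trigger. The action is that "treatment with IMO-8400 should be held and an anti-platelet antibody count obtained". Treatment can then be "resumed once pre-treatment criteria" (section 8.4.1) are satisfied. No dose level is named, and neither DLTs, DMEs nor section 6.5.2 is mentioned.

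Section 8.4.1 is a general condition on dosing: "IMO-8400 should not be administered until the following conditions are met". Its list is hemoglobin at least 7.5 g/dL, ANC at least 1,000/µL, platelets at least 50,000/µL, and other laboratory abnormalities at baseline or Grade 1 or lower. It says nothing about dose level.

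Section 6.3.1 includes "Grade 4 thrombocytopenia" among the laboratory DLT criteria, with no bleeding required. On causality, "Events will be considered DLT events unless they are unanimously assessed as" not related. Events that meet the definition but are "occurring after Week 5 of Cycle 1 are defined as dose modifying events" (DMEs).

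Section 6.5.2 covers patients with a laboratory DLT or a DME. They "may resume treatment after dose interruption and with dose modification if" every listed criterion is met:
- the dose is above 0.6 mg/kg/week, and patients at 0.6 mg/kg/week "will be discontinued";
- there has been no earlier interruption or adjustment for such an event;
- the Investigator and the Medical Monitor both consider continued treatment to be in the patient's interest;
- the abnormality improves by at least 2 grades, or to baseline, within 14 days of the last dose.

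Dosing then resumes at the next lowest level in Table-8.

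**The concern.** Section 6.5.5 is the section written for this event, so a site managing a severe platelet fall will turn to it first. It sends the reader only to 8.4.1, which is a set of laboratory thresholds. A site that stops there could restart a patient at 0.6 mg/kg/week whom 6.5.2 says must stop. At a higher level it could restart without stepping down, after a recovery that came too late, or for a second time.

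The situation is foreseeable. Patients may enter with platelets of 50,000/µL, the maximum duration of exposure is undefined (section 6.7), and 6.5.5 itself cites cases with another oligonucleotide 14 to 26 months after starting treatment. Events that late would be DMEs and so would fall under 6.5.2. What is at stake is the safety of individual patients. No endpoint, population or power figure is affected.

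**Working it through.** The plan states no figure to reproduce. The check sets the two restart rules side by side and then works out the dose consequence from Table-8.

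**Step 1: when both rules apply.** Section 6.5.5 applies when platelets fall below 25 x 10^9/L. Section 6.5.2 applies when the event is a laboratory DLT or a DME. They overlap when the fall is graded 4 and has not been unanimously assessed as unrelated. The protocol grades by NCI CTCAE v4.03 but does not print the platelet cut-offs, so how much of the 6.5.5 range is Grade 4 cannot be read from it. The rest of the check is limited to falls graded 4.

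**Step 2: the two rules in the overlap.**

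| Restart condition | 6.5.5 with 8.4.1 | 6.5.2 |
|---|---|---|
| At 0.6 mg/kg/week | can be resumed | discontinue |
| Restart dose above 0.6 | not stated | next lowest level |
| Time limit on recovery | none stated | 14 days from last dose |
| Earlier interruption for a laboratory DLT or DME | not mentioned | bars restart |
| Investigator and Medical Monitor agreement | not mentioned | required |

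**Step 3: an illustration at Level 1.** A patient on 0.6 mg/kg/week falls to 20 x 10^9/L (graded 4, not assessed as unrelated) and recovers to 55 x 10^9/L, with the other 8.4.1 criteria met. Since 55 is above 50, 6.5.5 allows restart. Section 6.5.2 requires discontinuation. Section 6.5.1 provides for resuming at a lower dose level, but Table-8 has none below 0.6 mg/kg. The two answers cannot both be followed.

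**Step 4: weekly exposure if a site restarted at an unreduced dose.** The ratio is the unreduced weekly dose divided by the weekly dose at the next lowest level.

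| Level | Unreduced (mg/kg/week) | Under 6.5.2 (mg/kg/week) | Ratio |
|---|---|---|---|
| 1 | 0.6 | 0 (discontinued) | not defined |
| 2 | 1.2 | 0.6 | 1.2/0.6 = 2 |
| 3 | 1.2 x 2 = 2.4 | 1.2 | 2.4/1.2 = 2 |
| 4 | 2.4 | 1.2 x 2 = 2.4 | 2.4/2.4 = 1 |
| 5 | 3.6 | 2.4 | 3.6/2.4 = 1.5 |

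Weekly exposure would differ at 4 of the 5 levels (1, 2, 3 and 5). At Level 4 only the dose per injection differs, 2.4 against 1.2 mg/kg. The figures for Levels 2, 3 and 5 are conditional, because 6.5.5 does not say that the dose stays the same.

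**Step 5: timing.** Recovery later than 14 days after the last dose bars restart under 6.5.2. Section 6.5.5 has no such limit. Read alone, it leaves only the rule in 6.5.2 and 8.4.2 that an interruption for toxicity of more than 21 days leads to discontinuation, and that rule allows exceptions by agreement.

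**The case against.** The strongest reply is that 6.5.5 lacks a cross-reference and nothing more. Section 6.5.2 applies by its own terms to every laboratory DLT or DME and makes no exception for platelets. Section 10.4.5 has treatment-emergent laboratory abnormalities assessed as potential DLTs, and 6.5.1 sends laboratory DLTs to 6.5.2. Section 6.5.5 is permissive, waives nothing, and has work of its own: the antibody test, and falls unanimously assessed as unrelated. Section 8.4.1 is a minimum for any dosing and is compatible with a stricter rule elsewhere. Section 6.5.1 also has the Investigator review restart decisions with the Medical Monitor, so a wrong restart needs both to overlook 6.5.2.

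Most of this stands. A reader might infer that 6.5.5 directs a full-dose restart at every level. The text does not support that, because it names no dose. A reader might also infer that nothing brings a 6.5.5 event under 6.5.2. That is not so either, given the scope of 6.5.2.

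The reply does not reach two things. At 0.6 mg/kg/week, permission to resume and an instruction to discontinue give different answers for the same patient. At every level, 6.5.5 offers the 8.4.1 thresholds as its only restart condition. The conditional phrase in 6.5.2 about dose modification being required does not remove the difference, because the opening sentence of 6.5.2 ties resumption to dose modification and the stop at 0.6 mg/kg/week is stated without qualification.

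**Conclusion.** The point holds as a minor inconsistency in patient-safety rules. For a platelet fall below 25 x 10^9/L that is graded 4 and not unanimously assessed as unrelated, 6.5.5 and 6.5.2 contradict each other at 0.6 mg/kg/week. At higher levels they can be reconciled, but 6.5.5 leaves out the step-down, the 14-day limit, the single-restart limit and the required agreement. The 1.5-fold and 2-fold exposure ratios show only what would follow from an unreduced restart. They do not describe what the protocol prescribes.

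The conclusion rests on the fall being Grade 4, a cut-off the protocol does not print. How often the two sections will meet cannot be estimated from the document; section 4.4.1 reports no grade 4 events among 19 patients treated as of August 2015. Medical Monitor review and the 21-day rule make a wrong restart less likely. It would also go too far to infer that DLT counts or dose-escalation decisions are distorted, since classification under 6.3.1 does not depend on 6.5.5.

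**What to change.** Add to section 6.5.5, after the sentence on resuming treatment: *Meeting the 8.4.1 criteria is necessary but not sufficient. If the event is a laboratory DLT or DME (6.3.1), restart is also subject to all criteria in 6.5.2, including discontinuation at 0.6 mg/kg/week and restart at the next lowest level.*

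The cost is two sentences in an amendment. No visit, test or procedure is added, and 6.5.5 continues to govern falls that are neither a DLT nor a DME.
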